9.1.2. Serious Adverse Events (SAEs)

A serious adverse event (SAE) is an untoward medical occurrence or effect associated with the use of a study drug at any dose, regardless of whether it is considered to be related to the study drug, which results in one of the following:

- Death (ie, all deaths on treatment or within 4 weeks after last study drug administration), including deaths due to disease progression. Any death occurring later than 4 weeks following the last dose should be reported as a serious adverse event whether it is a result of an event that started within the period covered by the on-study definition. The reported adverse event should be the event that caused the death. In addition, any adverse event resulting in death that occurs subsequent to the adverse event-reporting period and that the investigator assesses as possibly related to the study drug should also be reported as serious.
- Life-threatening adverse event. This is an event that, in the view of either the investigator or the sponsor, places the patient at immediate risk of death. It does not include an event that, had it occurred in a more severe form, hypothetically might have caused death.
- Inpatient hospitalization or prolongation of existing hospitalization (eg. excluding hospitalizations for administration of the study drug, procedures required by the study protocol, or CF-related diagnostic procedures; other planned hospitalizations; or hospitalizations related only to progression of disease). Please note that CF pulmonary exacerbations should be reported if they meet this criterion. Treatments in the emergency room for procedures such as hydration that do not require admitting the patient to the hospital and observational durations in the emergency room for less than 24 hours are not considered serious.
- Persistent or significant disability or incapacity or substantial disruption of the ability to conduct normal life functions.
- Any other medically important event that the investigator or the sponsor judges to be serious or which is defined as serious by the regulatory agency in the local country. Medical judgment should be exercised in deciding whether a reaction is serious in other situations. Important medical events that do not result in death, are not immediately life-threatening, and do not require hospitalization may be considered serious when, based on appropriate medical judgment, they may jeopardize the patient and may require medical or surgical intervention to prevent any of the outcomes listed above. Examples of such medical events include allergic bronchospasm requiring intensive treatment administration in an emergency room or at home, newly diagnosed malignancy, or blood dyscrasias, or convulsions that do not result in inpatient hospitalization, or the development of drug dependency or drug abuse.
- A pregnancy resulting in spontaneous abortion, stillbirth, neonatal death, or congenital anomaly [including that in an aborted fetus]).

Except for CF pulmonary exacerbations, an event need not be reported as a SAE if it exclusively represents a relapse or an expected change or progression of the baseline CF. This type of event need only to be reported as an adverse event.

Note that any SAEs occurring within 4 weeks of the date of last dose should be reported to the CRO Pharmacovigilance Unit if the investigator becomes aware of them.

In addition to serious adverse events, adverse events of special interest must be reported to the CRO Pharmacovigilance Unit within 24 hours. Adverse events of special interest include the following:

Laboratory abnormalities:

- Serum cystatin C >1.33 x ULN
- Serum creatinine > ULN for age
- Serum BUN >1.5 x ULN
- Urine dipstick with $\geq 2+$ blood
- Urine dipstick with $\geq 2+$ protein

Signs/symptoms:

- Dysuria
- Flank (renal) pain
- Nephrolithiasis or other urinary tract calculi

It should be noted that laboratory data sent to and analyzed by the Central Laboratory need not be reported through the CRO Pharmacovigilance Unit as these data will already be reported to PTC Therapeutics. Only those laboratory abnormalities meeting the protocol-defined criteria of an adverse event (ie, those that require clinical intervention or further investigation (beyond ordering a repeat [confirmatory] test), see Section 9.1.1) should be reported as adverse events in the appropriate CRF, whether they were analyzed by the central laboratory or another laboratory.

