6.3. Safety Monitoring and Study Drug Dose Interruption/Modification

6.3.1. Laboratory Abnormalities and Adverse Events Requiring Evaluation and Potential Drug Interruption/Modification

Patients must be monitored closely for adverse events or laboratory abnormalities during the course of the study.

For adverse events or laboratory abnormalities, the investigator will use judgment in determining whether the event or abnormality is clinically significant, whether diagnostic evaluation is warranted, and whether potential interruption of study drug treatment is appropriate. In general, life-threatening (Grade 4) or severe (Grade 3) adverse events or laboratory abnormalities should be considered clinically significant, although recurrent or persistent moderate events (Grade 2) may also be considered clinically significant in certain circumstances. Reference should be made to the Common Terminology Criteria for Adverse Events (CTCAE), Version 3.0 (see *http://ctep.cancer.gov/protocolDevelopment/electronic_applications/docs/ctcaev3.pdf* for grading the severity of adverse events and laboratory abnormalities.

Table 2 provides information on actions to be taken in the event that abnormalities are noted in specified laboratory parameters. Thresholds are provided for interrupting study drug immediately, for interrupting study drug after confirmation of a value beyond the threshold, or for continuing study drug while evaluating for potential drug-related toxicity. For adverse events or laboratory abnormalities not listed in Table 2, the investigator should use his/her judgment in determining whether the event or abnormality is clinically significant, whether diagnostic evaluation is warranted, and whether potential interruption of study drug is appropriate.

Organ System and Laboratory Parameter	Stop Study Drug Immediately, Confirm Abnormal Value, and Then Start Work-Up ^a	Stop Study Drug After Confirming Abnormal Value, and Then Start Work-Up ^a	Continue Study Drug, Confirm Abnormal Value, and then Start Work-Up ^a
Hepatic			
Serum total bilirubin ^b	≥Grade 3 (≥3.0 x ULN)	Grade 2 (1.5 – 3.0 x ULN)	
Serum ALT	≥Grade 3 (≥5.0 x ULN)	Grade 2 (>2.5 – 5.0 x ULN)	
Serum AST	≥Grade 3 (≥5.0 x ULN)	Grade 2 (>2.5 – 5.0 x ULN)	
Serum GGT	≥Grade 3 (≥5.0 x ULN)	Grade 2 (>2.5 – 5.0 x ULN)	
Renal			
Serum cystatin C	>2.00 mg/L	>1.33 – 2.00 mg/L	
Serum creatinine	≥ Grade 2 (≥1.5 x ULN for	Grade 1 (>ULN – 1.5 x ULN for	
Serum creatinine	age)	age)	

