6.3.2. Evaluation of Adverse Events or Laboratory Abnormalities

While specific monitoring, diagnostic testing, and supportive care measures must be instituted based on the clinical judgment of the investigator, investigators are encouraged to contact either the PTC Therapeutics medical monitor (or designee) to obtain guidance and to ascertain whether similar events are being seen at other investigator sites. The PTC Therapeutics medical monitor should be notified of any adverse event or laboratory abnormality that leads to dose interruption and should be apprised of ancillary laboratory or other diagnostic findings and the evolving data from any work-up of the initial abnormality. The PTC Therapeutics medical monitor may suggest review of the case with gastroenterology or nephrology consultants or with other experts (either at the site or retained by PTC Therapeutics).

Clinical evaluations for potential hepatic and renal toxicities may include the following:

- **Hepatic:** The medical history, hepatitis screening results, all clinical blood values (particularly serum bilirubin, GGT, AST, and ALT values), and all concomitant medications should be reviewed. Depending upon changes observed, the recommended diagnostic workup may include more frequent monitoring or further evaluations for viral hepatitis and immune disorders; tests for cholelithiasis; or abdominal ultrasound, computed tomography (CT), magnetic resonance imaging (MRI), or other imaging methods.
- **Renal:** The medical history, baseline ultrasound data, all clinical blood and urine renal values, serum electrolytes, medications, and potential pre- or post renal conditions should be reviewed. Depending upon the changes observed, recommended diagnostic workup may include further evaluations of blood or urine; tests of glomerular filtration rate (GFR), concentrating ability, or other renal functions; CT, MRI, or other imaging methods; and/or renal biopsy.

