9.9. Investigator Site Adverse Event Reporting Requirements

Classification of an event as serious or non-serious (see Section 9.1.2) determines the reporting procedures to be followed. Investigator site reporting requirements for adverse events are summarized in Table 6.

Classification	Reporting Time	Reporting Action
	Within 24 hours	Complete AE and SAE portions of CRF and notify site IRB/IEC, as per local IRB/IEC requirements. If unable to enter event in EDC, call the CRO Pharmacovigilance Unit or fax the back-up paper SAE report form to the CRO Pharmacovigilance Unit, within 24 hours.
Serious	Within 5 calendar days	Provide photocopies or document scan of relevant source documents ^a (eg, progress notes, nurses' notes, laboratory and diagnostic test results, discharge summaries) as requested by the CRO Pharmacovigilance Unit.
	Per CRF submission procedure	Record and submit information on appropriate CRFs (eg, Medical History and Concomitant Medications CRFs)
AESI	Within 24 hours	Complete AE and SAE portions of CRF and notify site IRB/IEC, as per local IRB/IEC requirements. If unable to enter event in EDC, call the CRO Pharmacovigilance Unit or fax the back-up paper SAE report form to the CRO Pharmacovigilance Unit, within 24 hours.
	Within 5 calendar days	Provide photocopies or document scan of relevant source documents ^a (eg, progress notes, nurses' notes, laboratory and diagnostic test results, discharge summaries) as requested by the CRO Pharmacovigilance Unit.
	Per CRF submission procedure	Record and submit information on appropriate CRFs (eg, Medical History and Concomitant Medications CRFs).
Nonserious	Per CRF submission procedure	Record and submit information on appropriate CRFs (eg, Adverse Events, Medical History and Concomitant Medications CRFs).

 Table 6. Investigator Site Reporting Requirements for Adverse Events

a Patient name, address, and other personal identifiers should be obscured.

Abbreviations: CRF = case report form, IRB/IEC = Institutional Review Board/Independent Ethics Committee, SAE = Serious Adverse Event

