- Serum Creatinine: Given the widespread clinical familiarity with serum creatinine as a marker of renal dysfunction and as a monitoring tool for nephrotoxins in clinical practice [Gilead 2002, Gilead 2006, Novartis 2005], characterization of serum creatinine provides an appropriate frame of reference relative to other experiences.
- Serum Cystatin C: An alternative to assessing GFR based on serum creatinine, serum cystatin C offers advantages in the assessment of renal function in the context of this protocol. Cystatin C is a low-molecular-weight {~13 kDa} proteinase inhibitor derived from all cells that is filtered by the glomerulus and degraded in the renal tubules [Herget-Rosenthal 2007]. The serum cystatin C concentration is almost solely dependent upon GFR and appears relatively unaffected by muscle mass or other conditions. An additional advantage is that circulating cystatin C changes more rapidly in response to multiple types of renal injury than creatinine [Herget-Rosenthal 2007]. Methods for measuring cystatin C are standardized and the correlations between serum cystatin C and GFR have been derived and confirmed in large studies involving healthy children and adults and those with renal dysfunction [Dharnidharka 2002, Grubb 2005, Zappitelli 2007]. Based on these considerations, values of serum cystatin above 1.33 mg/L should prompt diagnostic evaluation and interruption/modification of study drug if required per protocol.

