As necessary, laboratory abnormalities will be described by duration of study drug exposure, by dose, by age group, by sex, by race, by weight, and for special populations (eg, antibiotic use).

Table 2. Safety Monitoring Parameters and Actions To Be Taken

| Organ System and Laboratory Parameter | Stop Study Drug Immediately, Confirm Abnormal Value, and Then Start Work-Up ^a | Stop Study Drug After Confirming Abnormal Value, and Then Start Work-Up ^a | Continue Study Drug, Confirm Abnormal Value, and then Start Work-Up ^a | |
|--|---|--|--|--|
| Hepatic | | | | |
| Serum total bilirubin ^b | ≥Grade 3 (≥3.0 x ULN) | Grade 2 (1.5 – 3.0 x ULN) | | |
| Serum ALT | ≥Grade 3 (≥5.0 x ULN) | Grade 2 (>2.5 – 5.0 x ULN) | | |
| Serum AST | ≥Grade 3 (≥5.0 x ULN) | Grade 2 (>2.5 – 5.0 x ULN) | | |
| Serum GGT | ≥Grade 3 (≥5.0 x ULN) | Grade 2 (>2.5 – 5.0 x ULN) | | |
| Renal | | | | |
| Serum cystatin C | >2.00 mg/L | >1.33 – 2.00 mg/L | | |
| Serum creatinine | ≥ Grade 2 (≥1.5 x ULN for age) | Grade 1 (>ULN – 1.5 x ULN for age) | | |
| Serum BUN | ≥3.0 x ULN | ≥1.5 – 3.0 x ULN | | |

^a Laboratory abnormalities may be confirmed immediately or at the next scheduled clinic visit based on investigator judgment.

Abbreviations: ALT = alanine aminotransferase, AST = aspartate aminotransferase, BUN = blood urea nitrogen, GGT = gamma glutamyl transferase, ULN = upper limit of normal

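### The cystatin C trigger for an adverse event of special interest is set as a multiple of the ULN, while the stop-drug rule, its rationale and the SAP use 1.33 mg/L

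*Protocol*

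**What the plan says.** The AESI list in Protocol Section 9.1.2 contains the line "Serum cystatin C >1.33 x ULN". The same section states that "adverse events of special interest must be reported to the CRO Pharmacovigilance Unit within 24 hours".

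Every other use of the 1.33 cut-off is absolute:

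- Protocol Section 6.3.1, Table 2, stops drug after confirmation, followed by a work-up, at ">1.33 – 2.00 mg/L". Above 2.00 mg/L drug stops immediately.
- Protocol Section 14.2.4 gives the rationale, based on how cystatin C tracks GFR, and concludes that "values of serum cystatin above 1.33 mg/L should prompt diagnostic evaluation".
- SAP Section 4.10.2, Table 2, repeats the protocol's row: "Serum cystatin C | >2.00 mg/L | >1.33 – 2.00 mg/L".

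For an AESI, Protocol Section 9.9, Table 6, requires the site within 24 hours to "Complete AE and SAE portions of CRF and notify site IRB/IEC, as per local IRB/IEC requirements". A nonserious event follows the ordinary CRF submission procedure.

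**The concern.** One number carries two units, and the documents neither explain the difference nor give a cystatin C ULN that would reconcile them. The other two renal blood markers in the AESI list keep the scale of their Table 2 rows, so cystatin C is the only one that changes. A ULN multiple carried over from the neighbouring lines is a plausible explanation.

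What is at stake is how a site handles a renal signal. Renal toxicity is a leading safety concern for this drug: Section 14.2.4 reports that the renal serious adverse events in Study 009 occurred only on ataluren, and it prefers cystatin C partly because it responds to injury faster than creatinine. Under the present wording, a confirmed value that stops drug and starts a work-up could be filed as a routine nonserious event.

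**Working it through.** There is no plan figure to reproduce, so the check compares the rules and then converts the AESI trigger to mg/L.

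**Step 1. Lower limits of the renal blood markers.**

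| Marker | AESI list (Protocol 9.1.2) | Lowest stop-drug tier (Protocol Table 2) | Same scale? |
|---|---|---|---|
| Creatinine | above ULN for age | above ULN for age | yes |
| BUN | above 1.5 x ULN | at or above 1.5 x ULN | yes (differs only in > versus ≥) |
| Cystatin C | above 1.33 x ULN | above 1.33 mg/L | no |

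**Step 2. Conversion.** AESI trigger in mg/L = 1.33 x ULN. This equals 1.33 mg/L only when ULN = 1.33/1.33 = 1.00 mg/L. The ULN is not in the documents; the range 0.9 to 1.2 mg/L is an assumption. The stop-after-confirmation range in Table 2 is 2.00 - 1.33 = 0.67 mg/L wide.

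| Assumed ULN (mg/L) | AESI trigger (mg/L) | Stop-drug values that are not AESIs | Share of the 0.67 mg/L range |
|---|---|---|---|
| 0.9 | 1.33 x 0.9 = 1.197 | none | 0 |
| 1.0 | 1.33 x 1.0 = 1.330 | none | 0 |
| 1.1 | 1.33 x 1.1 = 1.463 | above 1.33 up to 1.46 | 0.133/0.67 = 20% |
| 1.2 | 1.33 x 1.2 = 1.596 | above 1.33 up to 1.60 | 0.266/0.67 = 40% |

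The shares are of concentration width. The documents give no distribution of cystatin C, so they cannot be read as shares of patients or events.

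**Step 3. Immediate-stop tier.** A value above 2.00 mg/L could miss AESI status only if 1.33 x ULN exceeded 2.00, that is if ULN > 2.00/1.33 = 1.50 mg/L.

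**Step 4. Does the classification change what the site does?** Scheduled biochemistry is analysed centrally (Protocol Section 8.2.11), and Section 9.1.2 exempts central-laboratory data from separate reporting through the CRO Pharmacovigilance Unit. The next sentence of that section still requires abnormalities that meet the adverse event definition to be entered: they "should be reported as adverse events in the appropriate CRF, whether they were analyzed by the central laboratory or another laboratory". Section 9.1.1 counts an abnormality as an adverse event when it needs investigation beyond a repeat test (unless it belongs to a clinical event already reported), and the work-up in Table 2 is such an investigation. The site must then choose between the AESI row and the nonserious row of Table 6, and the unit decides which.

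**Step 5. What does not depend on the unit.** Interruption follows Table 2. The medical monitor "should be notified of any adverse event or laboratory abnormality that leads to dose interruption" (Section 6.3.2). Central-laboratory values reach the sponsor in any case. The SAP frequency tables use the mg/L thresholds.

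**The case against.** The strongest reply accepts the mismatch and disputes its consequence.

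- **The harm rests on an unknown figure.** Values are missed only if the ULN is above 1.00 mg/L. This stands: the mismatch is certain, its direction is not.
- **The 24-hour effect is narrow.** Because cystatin C is measured centrally, the pharmacovigilance report is waived for scheduled samples. This also stands, but it does not remove the CRF duty in step 4, nor does it cover values from other laboratories.
- **Not every value in the range becomes an adverse event.** The work-up follows confirmation, and a footnote to Table 2 lets confirmation wait for the next scheduled visit, which can be 12 weeks away. An unconfirmed value may never need a report. This is correct, and it limits the point to confirmed values.
- **The analysis is protected.** SAP Section 4.10.1 tabulates and lists renal events leading to special diagnostic evaluation whatever their AESI status, and specifies no AESI table. This stands. Only the special attention that Protocol Section 11.4.5.1 gives to AESIs is touched.
- **The AESI and stop-drug lists need not match.** The AESI list adds dipstick findings and symptoms and omits the hepatic markers. But nothing suggests that a separate cystatin C limit was intended, and Section 14.2.4 derives the cut-off in mg/L.
- **It is late.** The SAP, dated July 2017, records early termination under a decision of 2 March 2017. If dosing has ended, an amendment would change little at sites.

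**Conclusion.** The concern holds. As written, the AESI trigger contradicts the protocol's own stop-drug rule and rationale, and the SAP. The size depends on a laboratory ULN that the documents do not give. Over the assumed range of 0.9 to 1.2 mg/L, between none and 40% of the width of the stop-after-confirmation range lies outside AESI status. The immediate-stop range is safe unless the ULN is above about 1.50 mg/L. The consequence is limited to AESI classification and expedited site reporting of confirmed values. It should be corrected because it is a safety decision threshold that is wrong as written, but it does not threaten the primary safety analysis.

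**What to change.** In Protocol Section 9.1.2, change the AESI line to serum cystatin C above 1.33 mg/L. The trigger then equals the lower edge of the Table 2 range for any laboratory ULN and the gap is zero. Table 2, Section 14.2.4 and the SAP stay as they are.

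The cost is a one-line protocol amendment, which under Section 13.2 needs IRB/IEC review. The one drawback arises if the ULN is below 1.00 mg/L, where AESI capture narrows: at 0.9 mg/L, values above 1.20 up to 1.33 mg/L would lose AESI status. Those values lie below the protocol's own work-up threshold, so little is lost. If dosing has already ended, use the mg/L limit when AESIs are classified retrospectively, and correct the line in any protocol that reuses this text.

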9.1.3. Unexpected Adverse Events

Unexpected adverse events are defined as those events that were not previously reported with study drug as referenced in the most current investigator brochure, or that are symptomatically and pathophysiologically related to a known toxicity but differ because of greater severity or specificity. For example, under this definition, hepatic necrosis would be unexpected (by virtue of greater severity) if the investigator brochure only referred to elevated hepatic enzymes or hepatitis. Similarly, cerebral thromboembolism and cerebral vasculitis would be unexpected (by virtue of greater specificity) if the investigator brochure only listed cerebral vascular accidents. "Unexpected," as used in this definition, also refers to an adverse event that is mentioned in the most current investigator brochure as occurring with the class of drugs or as anticipated from the pharmacological properties of the study drug, but is not specifically mentioned as occurring with the medicinal product.

For the purposes of considering expectedness, the ataluren investigator brochure provides a summary of the safety profile of ataluren based on available clinical information (also referred to as the reference safety information).

9.2. Eliciting Adverse Event Information

Each study patient will be questioned about adverse events at each post-screening study visit or during any telephone contact with the patient or parent/caregiver. The investigator is to report all directly observed adverse events and all adverse events spontaneously reported by the patient or parent/caregiver at each scheduled clinic visit after study drug administration or during any telephone contact with the patient or parent/guardian caregiver. The type of question asked should be open-ended, eg, *"How have you/ your child been feeling?"* or a similar type of query.

9.3. Adverse Event Recording

All adverse events (both serious and non-serious) that occur in patients during the adverse event reporting period must be recorded, whether or not the event is considered drug related. In addition, any non-serious, known untoward event that occurs subsequent to the adverse event reporting period that the investigator assesses as possibly related to the investigational drug/product should also be recorded as an adverse event.

All adverse events are to be recorded in the source documents and on the CRF using concise medical terminology; whenever possible terms contained in Medical Dictionary for Regulatory Activities (MedDRA) should be employed. In addition, the following information should be recorded:

- Indication of whether the event is serious or nonserious (see Section 9.1.2)
- Relationship to study drug (see Section 9.4)
- Severity of the event (see Section 9.5)
- Onset date
- Resolution date, or date of death
- Action taken
- Outcome of the event

Classification of the event as serious or nonserious determines the reporting procedures to be followed.

